1.0 PROTOCOL SUMMARY AND/OR SCHEMA

This is a double-blinded, randomized trial. Its purpose is to compare the steroid cream mometasone furoate 0.1% (MF), with standard emollient skin care, Eucerin, on the prevention of grade 2 or higher skin toxicities in breast cancer patients receiving PMRT to the chest wall and regional lymph nodes. Patients will be stratified based on two variables: the presence of a reconstruction in order to achieve a balanced population of patients being treated with either photon or electron beams, and body mass index (BMI <30 vs ≥30).

Female breast cancer patients who have received mastectomy + axillary surgery and will undergo postmastectomy radiation (PMRT) at our institution are eligible for this study. Enrollment of 143 patients is expected to take place over 3 years.

Skin toxicities using the Common Terminology Criteria for Adverse Events (CTCAE) v.4 scale will be scored by evaluating RN or MD . Assessments will be completed at baseline, weekly during radiation therapy (RT), and 10-14 days following the completion of RT. Patient-reported skin symptoms will also be assessed at baseline, at week 5 of RT, and 10-14 days following completion of RT.

Screening	Randomization	Pre-RT	Weekly During RT (5 weeks, 50 Gy)	Follow-up (10-14 Days Post-RT)
143 breast cancer patients status post mastectomy + axillary surgery, ± chemotherapy 
 Stratifications: 
 Reconstruction Yes vs no Body Mass Index <30 vs ≥30 	Eucerin BID 
 or mometasone furoate 0.1% BID 	
 Baseline H and P Baseline Provider Skin Toxicity Assessment Baseline Skindex-16 questionnaire Patient education on topical cream usage 	
 Weekly status checks Weekly skin cream compliance assessed Provider Skin Toxicity Assessment Skindex-16 questionnaire during Week 5 of RT 	
 Skin cream compliance assessed Provider Skin Toxicity Assessment Skindex-16 questionnaire

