3.2 Radiation-Induced Dermatitis

A variety of patient and treatment-related factors such as fractionation schedules, dose, size of the treatment field, concurrent chemotherapy, use of bolus or other beam-modifying devices, and individual genetic variation can affect the intensity of the skin reaction to radiation (Tucker, Turesson et al. 1992). The majority of data available regarding side effects are generated from patients receiving radiation to the intact breast, not the chest wall after mastectomy. Side effects are generally categorized as acute if occurring during or within 6 weeks of radiation treatment and late if occurring >6 weeks after completion of treatment. A common acute toxicity is dermatitis within the irradiated volume. Typically, the skin becomes erythematous and/or hyperpigmented, and may desquamate, in particular in the area of skin folds such as the axilla, supraclavicular fossa, or inframammary fold. Desquamation may be dry or moist. Progressive erythema may be seen after 10-20 Gy, depending on the fractionation schedule (Turesson and Notter 1975), and reaches maximal intensity approximately 1-2 weeks following the completion of treatment. An example of the development of moist desquamation and grade 2 erythema in a woman 1 week post-completion of PMRT to an unreconstructed chest wall is illustrated in Appendix 3.

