10.2 Evaluations After Radiation

Follow-up visits will be completed 10-14 days after the completion of RT. At this time, provider assessment of skin toxicity will be performed by the physician and RN, and the patient will complete another Skindex-16 form.

Tests and Observations	Consultation	Simulation	Set-Up/ Treatment #1	During Treatment (5 weeks)	10-14 Days Following Completion of Treatment (CoT)
History and Physical	X			Weekly Status checks	
Radiation Treatment Plan approval		X			
Randomization		X			
Patient Teaching and Administration of Topical Agent		X	X	Assess compliance weekly	
Provider Assessment of Skin Toxicity		X		Provider assessment weekly	X
Patient Assessment of Fitzpatrick Category (Appendix 2)		X			
Patient Assessment of Skin Toxicity (Appendix 1)		X		Week 5 only	X

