12.0 CRITERIA FOR THERAPEUTIC RESPONSE/OUTCOME ASSESSMENT

12.1 Assessment of Primary Objective

The grading of skin toxicity will be based on the CTCAE version 4.0 scale as defined in section 3.4. To ensure unbiased skin toxicity measurement, both the clinical team and patient will be blinded to the treatment assignment. The type of skin toxicity (moist desquamation or grade ≥ 2 erythema), maximal score, its location within the target (chest wall or axilla), and time to occurrence will be recorded weekly during RT and at week 2 follow-up on the Provider Skin Toxicity Assessment Form. Following the post-treatment visit, the patient will not need to return to the clinic for other follow-up visits unless otherwise specified by the treating physician.

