14.0 BIOSTATISTICS

This is a double-blinded, randomized trial (see Section 15.2 for details of randomization) to compare MF 0.1% cream with standard skin care (Eucerin) on the prevention of moderate to severe skin toxicities in breast cancer patients receiving post-mastectomy radiation to the chest wall and regional lymph nodes. A patient is deemed to have developed skin toxicity if she has a grade ≥ 2 skin toxicity as defined in Section 3.4 within 7 weeks from the beginning of radiation.

Based on estimates provided by radiation oncologists at our institution, the rate of grade ≥ 2 toxicity using Eucerin as skin care for chest wall radiation is $\approx 50\%$. This estimate is slightly lower than the findings from the Spierer study cited in section 3.2, to reflect this study's inclusion of patients treated with photons (in the presence of reconstruction) as well as electrons. We expect that the usage of MF can reduce this rate to 25%. 124 evaluable patients are needed for the comparison, with 62 patients in each arm. Two-sample, two-sided proportion tests will be used to derive the statistical significance. One interim analysis will be conducted when 31 patients in each arm have been enrolled and evaluated using the O'Brien-Flemming procedure, which will declare significance if the test p-value is less than 0.005. Correspondingly the final analysis will declare significance if the test p-value is less than 0.048. This design has a power of approximately 0.83 (i.e., detecting the true toxicity rate of 25% or lower) at the type I error (i.e., declaring MF more effective while it yields the same toxicity rate as Eucerin) rate of 0.05 based on 100000 statistical simulations.

All deaths unrelated to the toxicities, and patients lost to follow-up (before toxicities can be evaluated), will be excluded from the comparison and new patients will be accrued for replacement. To this end we plan to enroll an additional 15% of patients. Therefore our final proposed accrual is about 143 patients, which is expected to be done in 3 years.

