Patient-reported skin symptoms will be scored from the Skindex-16 surveys and compared between interventions using Wilcoxon tests at each separate assessment time point. Analysis of covariance may also be used when the baseline information is taken into account as a covariate. Multiple comparison tools will be employed to adjust for statistical significance levels. Maximum reported skin toxicities will be tabulated and summary statistics will be provided. Time to occurrence of skin toxicity will be handled by routine survival analysis such as Kaplan-Meier estimation, log-rank tests, and/or Cox regression models when comparisons are needed.

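### Section 14 sets no time scale or censoring rule for time to toxicity; if the survival methods are run on actual visit dates, the varying day of the single post-RT visit biases the Kaplan-Meier curve upward

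*Combined protocol and SAP*

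**What the plan says.** Time to occurrence of skin toxicity belongs to the second secondary objective (Section 2.0). Section 14.0 gives its analysis in one sentence: "Time to occurrence of skin toxicity will be handled by routine survival analysis such as Kaplan-Meier estimation, log-rank tests"; the sentence goes on to name Cox models, with comparisons made as needed.

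The schema in Section 1.0 places skin assessments at baseline, "weekly during radiation therapy (RT), and 10-14 days following the completion of RT", with RT lasting 5 weeks. Section 10.2 repeats the last time point: "Follow-up visits will be completed 10-14 days after the completion of RT". Section 12.1 says that "time to occurrence will be recorded weekly during RT and at week 2 follow-up", and that no further study visit is needed after the post-treatment one.

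Section 3.2 says that erythema "reaches maximal intensity approximately 1-2 weeks following the completion of treatment". For the primary endpoint, Section 14.0 counts a grade 2 or higher toxicity "within 7 weeks from the beginning of radiation" and compares proportions.

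No section defines the event time, the censoring time or the time scale for the survival analysis, and none mentions interval censoring.

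**The concern.** Onset is never observed directly. It lies somewhere between the last negative and the first positive assessment. During RT that interval is about a week. The final interval is longer: if the last weekly check falls 0 to 4 days before the final fraction, it runs from 10 to 14 + 4 = 18 days, and it covers the stated time of peak reaction.

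The usual right-censored coding dates an event to the visit that found it and censors an event-free patient at her last assessment. Here both happen at the same post-RT visit, whose day varies for scheduling reasons. Event-free patients seen on day 10 are removed before the events found on days 11-14 are counted. Patients due later meanwhile count as event-free although nobody has examined them. Each later event is then divided by a shrinking denominator, although every patient had the same single look.

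At stake is the reported curve for a stated secondary objective, which could end well above the proportion of patients who had the toxicity. Some power is also at stake, because the log-rank and Cox comparisons would order patients partly by appointment day.

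**Working it through.** **The plan's own figure.** The documents give no figure for the time-to-occurrence analysis. The primary power of about 0.83 (62 per arm, 50% v 25%) reproduces: 0.828 at two-sided 0.05, 0.824 at 0.048, and 0.835 by simulation of the two-look rule with a pooled z-test without continuity correction. That test uses no event times.

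**Inputs from the documents.** Rates of 50% and 25% and 62 patients per arm (Section 14.0); 5 weeks of RT (Section 1.0); post-RT visit on days 10-14 (Section 10.2).

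**Assumptions.**
- The share *s* of toxicities first seen at the post-RT visit is not given, so it is varied from 0% to 100%.
- Visit days are spread evenly over days 10-14.
- Time is the visit date, and event-free patients are censored on that date.
- RT has either one fixed length (5 distinct final days) or takes 32 or 34 calendar days according to starting weekday (7 distinct final days).

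**Formula.** With true rate π, the proportion positive during RT is π(1 − s). Among those still event-free, the proportion positive at the post-RT visit is q = πs / [1 − π(1 − s)]. With one visit time, survival is multiplied by (1 − q), and the curve ends at π. With five equally used days, the risk set falls through 5/5, 4/5, 3/5, 2/5 and 1/5, so survival is multiplied by the product of (1 − q/k) for k = 1 to 5.

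**Example, π = 50%, s = 50%.** During RT 25% are positive, and q = 0.25/0.75 = 0.333. The product is 0.667 × 0.833 × 0.889 × 0.917 × 0.933 = 0.4225. The curve ends at 1 − 0.75 × 0.4225 = 68%.

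**Example, π = 50%, s = 20%.** During RT 40% are positive, and q = 0.10/0.60 = 0.167. The product is 0.668. The curve ends at 1 − 0.60 × 0.668 = 60%.

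End of the Kaplan-Meier curve on visit dates, no treatment breaks (5 / 7 distinct days):

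| Share *s* | True 50% | True 25% |
|---|---|---|
| 0% | 50 / 50% | 25 / 25% |
| 20% | 60 / 61% | 31 / 32% |
| 50% | 68 / 70% | 38 / 40% |
| 60% | 70 / 72% | 40 / 42% |
| 100% | 75 / 78% | 46 / 49% |

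Coded by scheduled visit, the curve ends at 50% and 25% in every row.

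**Treatment breaks (sensitivity).** Breaks of 3-7 days were assumed in 31% of patients, with 7 distinct days before breaks and a true rate of 50% (2,500 runs). The curve ends at 68% (s = 20%) or 81% (s = 50%). Read at day 49, it shows only 52-53%, because about 21% of final visits fall after day 49 and those patients are still in the risk set.

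**Log-rank power.** 6,000 simulated trials per row, 62 per arm, 50% v 25%, two-sided 0.05. Events seen during RT were assumed to fall in weeks 2-5 with weights 0.05, 0.15, 0.35 and 0.45.

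| Share *s* | Visit date (7 days) | Scheduled visit | Loss in points, 7 days (5 days) |
|---|---|---|---|
| 20% | 0.820 | 0.829 | 0.9 (0.4) |
| 50% | 0.794 | 0.830 | 3.5 (3.4) |
| 80% | 0.735 | 0.811 | 7.6 (8.4) |
| 100% | 0.711 | 0.838 | 12.7 (12.7) |

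Losses were computed before rounding. With both rates at 50% and s = 50%, the type I error is 0.055 on visit dates and 0.053 by scheduled visit.

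**The case against.** The strongest reply is that the plan never says visit dates will be used. Section 12.1 has time recorded by week and at a week 2 follow-up, Section 12.2 speaks similarly, and the primary endpoint has a common 7-week horizon. Coding by week, or censoring every event-free patient at one common day, removes the inflation entirely. This stands, and it makes the point conditional. It does not remove it: the plan adopts neither rule, and the ordinary reading of a right-censored analysis leads to the biased coding.

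The size is also uncertain. Section 3.2 says when the reaction peaks, not when grade 2 is first reached, and it notes erythema after 10-20 Gy, early in a 50 Gy course. A small share first seen at the post-RT visit is therefore possible. This stands too, so only a range can be given.

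The weekly checks cause none of the inflation, because nobody is censored between them. The power loss is small in mid-range cases and concerns a secondary comparison that the trial is not sized for.

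A reader might infer that the trial will report about 70% toxicity when 50% is true. The documents do not support that: it needs visit-date coding, roughly 50-60% of events first seen after RT, and a curve read at its end. A reader might also infer that the curve would contradict the primary result. That does not follow either. The primary test compares crude proportions, and in these scenarios both arms shift upward and keep their order.

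**Conclusion.** The concern holds in conditional form. Event times are known only to an interval, and Section 14.0 has no rule for this. If visit dates are the time scale and event-free patients are censored at the post-RT visit, the Kaplan-Meier curve is biased upward by the spread in that visit's day. Without treatment breaks, the end of the curve for a true 50% lies anywhere from 50% to 78%, depending on a share that the documents do not state and on the assumed even spread of visit days. With assumed breaks, the bias is large at the end of the curve but only 2-3 points at day 49.

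The log-rank loss runs from 1 point or less (share 20%) to about 13 points (share 100%). Type I error stays near nominal provided both arms share the same visit pattern. The primary analysis and its power are not touched. This is a change worth making to a secondary analysis, because an unstated coding choice decides whether the curve is right and a better choice is available at little cost.

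**What to change.** In Section 14.0, define time to grade 2 or higher toxicity by scheduled assessment: RT weeks 1-5, then the post-RT visit. State the censoring rule on the same scale. Report cumulative incidence by visit, and compare arms with a log-rank test on visit number or a discrete-time model. Alternatively, use interval-censored methods with the interval from last negative to first positive assessment. Report the crude proportion as the toxicity rate, rather than the end of a Kaplan-Meier curve.

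The log-rank test on visit number stays within the methods already named, so one or two sentences may be enough. The cost is that wording and light programming, with no new data, visits or patients. The downside is that timing is reported by visit rather than by day, which is the resolution that the schedule provides.

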15.0 RESEARCH PARTICIPANT REGISTRATION AND RANDOMIZATION PROCEDURES

15.1 Research Participant Registration

Confirm eligibility as defined in the section entitled Criteria for Patient/Subject Eligibility.

Obtain informed consent, by following procedures defined in section entitled Informed Consent Procedures.

During the registration process registering individuals will be required to complete a protocol specific Eligibility Checklist.

MEMORIAL SLOAN-KETTERING CANCER CENTER IRB PROTOCOL

IRB#: 13-069 A(1)

All participants must be registered through the Protocol Participant Registration (PPR) Office at Memorial Sloan-Kettering Cancer Center. PPR is available Monday through Friday from 8:30am – 5:30pm at [contact]. Registrations must be submitted via the PPR Electronic Registration System (<http://ppr/>). The completed signature page of the written consent/RA or verbal script/RA, a completed Eligibility Checklist and other relevant documents must be uploaded via the PPR Electronic Registration System.

15.2 Randomization

Randomization will be done at MSKCC. Patients will be randomized to the MF 0.1% cream arm or the standard skin care arm with Eucerin at the ratio of 1:1. For patients enrolled at MSKCC, after eligibility is established and immediately after consent is obtained, the RSA will register participants in the PPR system and randomize participants using the Clinical Research Database (CRDB), by calling the MSKCC PPR Office at [contact] between the hours of 8:30 am and 5:30 pm, Monday to Friday. Randomization will be accomplished by the method of random permuted block, and will be stratified by the presence of breast reconstruction and BMI. After treatment arm is determined by randomization, RSAs at MSKCC will notify the research staff of the participant ID via email within 24 hours of randomization. Since this is a double blind study, the research participants' treatment assignments can be viewed in the CRDB only by the hospital pharmacists who are dispensing the study drugs.

15.3 Blinding

Study drug containers will appear identical with assigned numbers divided evenly between study drug and control. Details of which drug is associated with each number will be recorded in a logbook. When a patient is assigned to a treatment arm based on the process outlined in section 15.2, the pharmacist will obtain a number assignment from CRDB, re-label the cream and keep a log recording the number of the jar dispensed.

16.0 DATA MANAGEMENT ISSUES

An RSA will be assigned to the study, whose responsibilities will include project compliance, data collection, abstraction and entry, data reporting, regulatory monitoring, problem resolution and prioritization, and coordinating the activities of the protocol study team.

The data collected for this study will be entered into a secure database. Source documentation will be available to support the computerized patient record.

16.1 Quality Assurance

Weekly registration reports will be generated to monitor patient accruals and completeness of registration data. Routine data quality reports will be generated to assess missing data and inconsistencies. Accrual rates, and extent and accuracy of evaluations and follow-up, will be monitored periodically throughout the study period and potential problems will be brought to the attention of the study team for discussion and action.

16.2 Data and Safety Monitoring

The Data and Safety Monitoring (DSM) Plans at MSKCC were approved by the National Cancer Institute (NCI) in September 2001. The plans address the new policies set forth by the NCI in the document entitled "Policy of the National Cancer Institute for Data and Safety Monitoring of Clinical Trials," which can be found at <http://deainfo.nci.nih.gov/grants/policies/datasafety.htm>. The DSM Plans at MSKCC were established and are monitored by the Office of Clinical Research. The MSKCC DSM Plans can be found on the MSKCC Intranet at <http://mskweb2.mskcc.org/irb/index.htm>.

There are several different mechanisms by which clinical trials are monitored for data, safety, and quality. There are institutional processes in place for quality assurance (e.g., protocol monitoring, compliance and data verification audits, therapeutic response, and staff education on clinical research quality assurance) and departmental procedures for quality control, plus there are two institutional committees that are responsible for monitoring the activities of our clinical trials programs: the Data and Safety Monitoring Committee for Phase I and II clinical trials, and the Data and Safety Monitoring Board for Phase III clinical trials, reporting to the Center's Research Council and Institutional Review Board (IRB).

During the protocol development and review process, each protocol will be assessed for its level of risk and degree of monitoring required. Every type of protocol (e.g., National Institutes of Health sponsored, in-house sponsored, industrial sponsored, NCI cooperative group, etc.) will be addressed and the monitoring procedures will be established at the time of protocol activation.

17.0 PROTECTION OF HUMAN SUBJECTS

The procedures involved in this study are felt to be of minimal risk, meaning that the probability and magnitude of harm or discomfort anticipated in the research are not greater in and of themselves than those ordinarily encountered in daily life or during the performance of routine physical or psychological examinations or tests. The benefit derived from the study would be prevention of moderate to severe skin toxicities in breast cancer patients undergoing chest wall radiation. Patients or their legal guardians will receive comprehensive explanation of the proposed treatment options being offered on this protocol, including the nature of the investigation, rationale, alternative treatments and any known previously observed side effects, the investigational nature of the study, and the potential benefits and risks of the intervention. Participation in this trial is voluntary. All patients will be required to sign a statement of informed consent, which must conform to IRB guidelines.

17.1 Privacy

MSKCC's Privacy Office may allow the use and disclosure of protected health information pursuant to a completed and signed Research Authorization form. The use and disclosure of protected health information will be limited to the individuals described in the Research Authorization form. A Research Authorization form must be completed by the Principal Investigator and approved by the IRB and Privacy Board (IRB/PB).

17.2 Serious Adverse Event (SAE) Reporting

Any SAE must be reported to the IRB/PB as soon as possible but no later than 5 calendar days. The IRB/PB requires a Clinical Research Database (CRDB) SAE report be submitted electronically to the SAE Office at [contact]. The report should contain the following information:

Fields populated from CRDB:

- Subject's name (generate the report with only initials if it will be sent outside of MSKCC)
- Medical record number
- Disease/histology (if applicable)
- Protocol number and title

Data needing to be entered:

- The date the adverse event occurred
- The adverse event
- Relationship of the adverse event to the treatment (drug, device, or intervention)
- If the AE was expected
- The severity of the AE
- The intervention
- Detailed text that includes the following
 - A explanation of how the AE was handled
 - A description of the subject's condition
 - Indication if the subject remains on the study
 - If an amendment will need to be made to the protocol and/or consent form.

The PI's signature and the date it was signed are required on the completed report.

